5: Will occur at alltime points stated even if participant is off infusion but still in hospital. Only done when possible given clinician and time constraints.

6.0 Data and Specimen Banking

6.1 Storage and Access:

Blood will be obtained at three different time points (0, 24 hours, and 72 hours) and will be coupled with clinical care blood draws when possible. These samples will be stored in a -80°C freezer in lab space utilized by the PACCS division at the University of Minnesota for future analysis. Serum, RNA, and cell lysates will be separated and stored with study code only.

6.2 Data:

Specimens will be stored by study code. All study data will be associated with the specimen through the study code link.

6.3 Release/Sharing:

Data will be shared with other researchers who request it, under the following conditions:

- Requester provides protocol and IRB approval or Determination of Non-Human Subjects Research.
- Requester completes Data Use Agreement form as developed by the Health Information Privacy and Compliance Office at the University of Minnesota.
- Any data or specimen can be shared but all identifiers will be stripped. Requester will not be provided with link between identity and study code.

7.0 Sharing of Results with Participants

Not applicable. No results will be shared with participants.

8.0 Study Duration

Each participant will be on the study drug for up to four days. There is a final data collection time point at 28 days but no participant interaction is needed for this; it will be chart review only.

It is expected that it will take up to 1.5 years to enroll all study participants. It is expected that it will take up to 2 years to complete all study procedures and data analysis.

9.0 Study Population

9.1 Inclusion Criteria:

- Capability to provide written consent from participant or legally authorized representative (LAR) if the participant is unable or incapacitated due to severity of illness.
- Age \geq 18 years
- Septic shock as pragmatically defined as:
 - Order for intravenous antimicrobials with either procalcitonin $>$ 2 ng/mL within 24 hours of enrollment OR other clinical suspicion of infection or confirmed infection AND
 - Hypotension requiring vasopressor therapy, despite fluid resuscitation of at least 30 mL/kg ideal body weight AND
 - Lactate $>$ 2 mmol/L 24 hr prior to enrollment AND

- Presence of sepsis defined as equal to or greater than 2 SIRS criteria and/or acute increase in qSOFA score of 2 points or more.
 - *SIRS criteria: 1) Temperature greater than 38° or less than 36° Celsius. 2) Heart rate greater than 90 beats per minute. 3) Respiratory rate greater than 20 breaths per minute OR arterial carbon dioxide tension less than 32 mmHg. 4) White blood cell count greater than 12,000 cell/ μ L, less than 4,000 cells/ μ L, OR band cells greater than 10% of the total white blood cell population.*
 - *qSOFA: 1 point each is assigned for: 1) systolic blood pressure below 100, 2) respiratory rate greater than 22, and 3) mental status not at baseline.*

9.2 Exclusion Criteria:

- Unable to start infusion within 24 hours of septic shock identification
- Currently pregnant or breastfeeding
- Patient to receive comfort measures only
- Cardiac Arrest
- Cardiovascular Surgery patients receiving prophylactic peri-operative antibiotics < 48 hours post-operation
- Participation in another study involving an investigational product within 30 days of the baseline visit
- Allergy to Vitamin C
- History of nephrolithiasis
- History of G6PD deficiency
- ESRD patients, transplant eligible on dialysis currently taking vitamin C supplementation
- Clinical course that treating clinician decides would preclude safe participation

9.3 Screening:

Potential participants will be identified by clinic staff at sites identified in Section 23.0. Once identified, the study team will review the medical record for basic eligibility and research opt-out status. Once the medical record has been reviewed, the investigator or coordinator and floor staff will approach the potential participant to explain the study.

10.0 Vulnerable Populations

10.1 Vulnerable Populations:

- Children
- Pregnant women/Fetuses/Neonates
- Prisoners
- Adults lacking capacity to consent and/or adults with diminished capacity to consent, including, but not limited to, those with acute medical conditions, psychiatric disorders, neurologic disorders, developmental disorders, and behavioral disorders
- Approached for participation in research during a stressful situation such as emergency room setting, childbirth (labor), etc.

- Disadvantaged in the distribution of social goods and services such as income, housing, or healthcare
- Serious health condition for which there are no satisfactory standard treatments
- Fear of negative consequences for not participating in the research (e.g. institutionalization, deportation, disclosure of stigmatizing behavior)
- Any other circumstance/dynamic that could increase vulnerability to coercion or exploitation that might influence consent to research or decision to continue in research
- Undervalued or disenfranchised social group
- Members of the military
- Non-English speakers
- Those unable to read (illiterate)
- Employees of the researcher
- Students of the researcher
- None of the above

10.2 Adults lacking capacity to consent and/or adults with diminished capacity to consent:

Patients who are in septic shock often have brain dysfunction or encephalopathy. This dysfunction is part of the sepsis syndrome and medical care often involves the use of surrogates to make urgent medical decisions for them. The same surrogates will act as an LAR for this study so they will be well versed in what this means, consenting to something for the participant. Those experiencing brain dysfunction are often those who are experiencing more severe symptoms of septic shock and thus, are those who would be most benefited by the use of this treatment. There are no additional risks for enrolling participants who cannot consent for themselves.

10.3 Additional Safeguards: Not applicable.

No individuals (pregnant women, neonates, nor prisoners) required additional safeguards will be enrolled.

11.0 Local Number of Participants

11.1 Local Number of Participants to be Consented:

Approximately 140 (70 per group) will be enrolled for an expected 124 (62 per group) for the final analysis. As there is a rolling startup for the sites, it is expected that the largest number of participants will be from Fairview Southdale.

12.0 Local Recruitment Methods

12.1 Recruitment Process:

Potential participants will be recruited from the ICU by study investigator after identified by intensivist physician on the floor or made aware of septic patient elsewhere in the hospital. Recruitment will take place at any time when a study investigator or trained coordinator is available for a consenting discussion and eligibility review. The investigator or other study team member will review opt-out status and medical records for basic eligibility before approaching the candidate. Once basic eligibility has been established, the investigator or coordinator and floor staff as necessary will approach the candidate.

12.2 Source of Participants:

Potential participants will be sourced from all patients admitted to the adult ICU with diagnostic criteria for septic shock who have not opted out of research. It is expected that participants could present to the ICU from either the emergency department or another floor or unit in the hospital. Please see Section 23.0 for list of sites.

12.3 Identification of Potential Participants:

Potential participants will be identified by the intensivist physician and study clinicians as those already admitted to the hospital for septic shock or suspicion of septic shock. Medical records will be reviewed for research opt-out status.

12.4 Recruitment Materials:

Not applicable. No recruitment materials to be used.

12.5 Payment:

No compensation or other payment will be provided to participants.

13.0 Withdrawal of Participants

13.1 Withdrawal Circumstances:

Participants can be withdrawn from the infusion or the study completely at any time by the study clinician or their personal clinician for:

1. A serious adverse event suspected to be related to the study drug.
2. Any suspicion that further involvement would jeopardize medical care.
3. Transitioning to comfort care measures only

Unblinding of treatment allocation will occur when such information would be critical to the ongoing care of the participant. Researchers will work with IDS and the research pharmacist on the unblinding procedures.

13.2 Withdrawal Procedures:

At the point of a participant-requested withdrawal, the infusion will be halted and no further direct interaction will occur. Data collection including Day 28 medical record review will still be conducted.

13.3 Termination Procedures:

Data will continue to be used and analyzed after withdrawal or termination.

14.0 Risks to Participants

14.1 Foreseeable Risks:

Vitamin C risks: Vitamin C has a good safety profile as evidenced in the background section of this proposal. Participants will be educated about potential adverse effects as part of the consent process, including inquiries about daily use of multi-vitamins, nutritional supplements or powders, or anything else that might contain vitamin C. Investigators will include known comorbidities that could affect vitamin C risk including kidney stones, diabetes, and cancer in their review of general eligibility. These would not make somebody automatically ineligible but would factor into a general clinical decision on whether or not it would be safe to enroll them.

There are no known major risks at the dose used in this study, approximately 6,000 milligrams per day to a total culminated dose of 25 grams. A tolerable upper limit of 2,000 milligrams per day oral administration was published in 2000³¹. At ingestions higher than 3,000 milligrams per day the most common adverse effect is diarrhea, but can include nausea, vomiting, heartburn, stomach cramps, and headaches. Clinical studies using dosing greater than 100,000 milligrams per day intravenously¹⁴, administered as quickly as 1g/min³² have been well tolerated, with no indication of harm following administration¹⁴. Hyperoxaluria and oxalate nephropathy have been reported in an individual status post renal transplant who previously had taken daily vitamin c supplementation whilst on dialysis³³, though additional studies suggest that ascorbic acid does not contribute to renal oxalate stone formation^{34,35}.

Blood draw risks and IV: The risks associated with the blood draw include minimal discomfort, and/or bruising. In very rare cases, a small blood clot can form at the site of the needle insertion. The risks of the intravenous line are similar to a blood draw but because it is kept in the vein for a longer period of time, the risk of bruising and discomfort are slightly higher. All participants will have an peripheral or central intravenous line catheter placed for standard of care medications and will have clinical blood drawn on at least a daily basis. Any research blood draw or IV placed for the infusion will be coupled with clinical care when possible.

General participation risks: There is always the risk for a breach of confidentiality during the course of any research study.

14.2 Reproduction Risks:

Not applicable. Because Vitamin C in doses exceeding RDA recommendations is classified as category C in pregnancy (insufficient evidence to determine safety), pregnant and breast-feeding women will be excluded.

14.3 Risks to Others:

Not applicable. No risk to others.

15.0 Potential Benefits to Participants

15.1 Potential Benefits:

No direct guaranteed benefit to individual participants.

16.0 Data Management

16.1 Data Analysis Plan:

Patient baseline characteristics will be summarized and presented using means and standard deviations for continuous variables and frequencies and percentages for categorical variables. Treatment groups will be compared using two-sample t test for continuous variables and Chi-square test for categorical variables.

Analysis plan for Aim 1: Mortality rates between treatment groups will be compared using Chi-square test. Logistic regression model will be used to model the probability of death. Model will include treatment group and covariates determined by the investigators to impact mortality and/or those that are significantly different between groups at baseline.

Analysis plan for Aim 2: Clinical outcomes at ICU discharge will be compared between groups using two-sample t test for continuous variables and Chi-square test for categorical variables. Multivariate linear and logistic regression analysis will be performed for continuous outcomes and dichotomous outcomes respectively to adjust for covariates.

Analysis plan for Aim 3: Correlation analysis will be conducted to examine the association between clinical characteristics and Vitamin C responsiveness.

Intention-to-treat analysis will be used. Analysis will be performed using Statistical Analysis Software (version 9.3, SAS Institute Inc., Cary, NC).

16.2 Power Analysis:

The trial will enroll enough participants to demonstrate a 20% mortality difference in between treatment groups. Based on this information, 124 patients, 62 patients in each arm, would be needed to have an 80% power to detect a 20 % decrease in hospital mortality between the two groups with a two-tailed alpha error of 0.05. To account for potential dropout of participants, planned enrollment will be 70 per arm, 140 total.

16.3 Data Integrity:

REDCap™ data will be periodically reviewed by the regulatory specialist and project manager or coordinator; to occur at the request of the PI and before final analysis occurs. Standard data quality checks will be run using REDCap™'s integrated programs.

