3.0 Study Endpoints/Events/Outcomes

3.1 Primary Endpoint/Event/Outcome:

First outcome endpoint for Specific Aim 1: all-cause mortality measured at ICU discharge.

Second outcome endpoint for Specific Aim 1: all-cause mortality measured at 28 days post Day 0.

3.2 Secondary Endpoint(s)/Event(s)/Outcome(s):

Outcome endpoint for Specific Aim 2: Difference in clinical outcomes between both groups at ICU discharge. Specific secondary endpoints may include, depending on power and final enrollment:

- a. Duration of vasopressor therapy post administration of Vitamin C (or placebo). Conclusion of vasopressor therapy will be defined as the time point when pressors are stopped, following which they are not restarted for 24 hours.
- b. Duration of ICU stay post administration of Vitamin C (or placebo).
- c. Time to lactate clearance post administration of Vitamin C (or placebo). Time of lactate clearance will be defined as the first time point at which measured lactate level drops below the normal level as defined by the measuring laboratory.
- d. Rate of lactate and procalcitonin clearance over 24, 48 and 96 hours following Vitamin C (or placebo) administration (in patients for whom values are available). Defined as the change in lactate and procalcitonin level from the initial measurement to the measurement at the designated time point if available, or closest measurement within 4 hours of the designated time point.
- e. Duration of mechanical ventilation post administration of Vitamin C (or placebo). Cessation of mechanical ventilation will be defined as the time of extubation following which re-intubation is not required for a full 24 hours.
- f. Incidence of need for renal replacement therapy during the 96 hour drug administration period
- g. Change in serum creatinine at 24, 48, 72, and 96 hours after Vitamin C (or placebo) administration compared to level at enrollment (in patients for whom values are available). The measurement closest in time to the designated time-point (within 12 hours) will be used. Patients who are dialysis-dependent at baseline or are currently receiving renal replacement therapy will be excluded from this endpoint.
- h. Change to SOFA and/or APACHE scores from initiation of Vitamin C (or placebo) as measured at 24, 48, 72, and 96 hours.

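### Durations of vasopressors, ICU stay and ventilation, and time to lactate clearance, are compared by t test without a workable rule for death, so a mortality difference would be mixed into them

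*Combined protocol and SAP*

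**What the plan says.** Section 3.2 frames the Aim 2 endpoint as "Difference in clinical outcomes between both groups at ICU discharge". It then lists items under a conditional lead-in: "Specific secondary endpoints may include, depending on power and final enrollment". Four of them are times from the start of study drug to an event:

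- **Item a, vasopressor duration.** "Conclusion of vasopressor therapy will be defined as the time point when pressors are stopped, following which they are not restarted for 24 hours".
- **Item b, ICU stay.** No end rule is written. However, the first primary endpoint in Section 3.1 is mortality at ICU discharge, so discharge in this protocol has to include leaving the unit by death.
- **Item c, time to lactate clearance.** It ends at the first lactate below the laboratory's normal level. Nothing is said about lactate that never gets there.
- **Item e, ventilation duration.** It ends at an extubation that holds for 24 hours. Nothing is said about death while intubated.

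For Aim 2, Section 16.1 states: "Clinical outcomes at ICU discharge will be compared between groups using two-sample t test for continuous variables". It then adds: "Multivariate linear and logistic regression analysis will be performed for continuous outcomes and dichotomous outcomes respectively to adjust for covariates". The analysis population is one sentence: "Intention-to-treat analysis will be used". The document contains no censoring rule, time-to-event method, survivors-only definition or score for deaths. Section 16.2 sizes the trial at 62 per arm for a 20% "decrease in hospital mortality between the two groups with a two-tailed alpha error of 0.05".

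**The concern.** Each of these items is meant to show recovery: off pressors, off the ventilator, lactate normal, out of the ICU. Death can come first, and an intention-to-treat statement does not supply a number for someone who never recovers. The analyst is left with two routes under the stated t test.

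- **Let death end the clock.** Early deaths then score as short durations, which look like good outcomes. The difference in means carries the mortality difference with it.
- **Drop participants without an event.** The groups compared are then no longer the randomised ones, because treatment may have changed who survives to have a value.

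Either route can move the result when treatment has no effect on recovery, and the choice could be made after the data are seen. The Study Summary gives resolution of shock as the secondary objective, and item a seems the closest measure of it (my inference; the protocol does not define one by the other). Section 18.2 also sends Aim 2 results to the DSMB.

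**Working it through.** **1. The plan's own figure.** Section 16.2 gives 62 per arm, 80% power, two-sided alpha 0.05 and a 20% decrease, but no control rate. Using the pooled-variance formula for two proportions, with p̄ the mean of the two rates,

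n = [1.96·√(2p̄(1−p̄)) + 0.842·√(p₁(1−p₁) + p₂(1−p₂))]² / (p₁−p₂)²

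- 30% vs 10% gives 61.6, that is 62 per arm.
- 25% vs 5% gives 48.8; 40% vs 20% gives 81.2; 50% vs 30% gives 93.0.
- A relative 20% reduction would need 388 per arm (control 50%) to 1,094 per arm (control 25%).

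So the stated size fits an absolute 20-point difference near 30% vs 10%. The 25% to 50% in Section 2.1 is a background rate, not a design input.

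**2. Shift when death ends the clock.** Let s and d be the mean durations in survivors and in deaths, the same in both arms (no effect on recovery), and p the proportion whose death precedes the event. The mean in an arm is (1−p)s + pd, so

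vitamin C − placebo = (p_T − p_C)(d − s)

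The documents give no durations, so s and d are assumptions. The significance rates are from 20,000 simulated trials, 62 per arm, gamma-distributed durations with shapes 1, 2 and 4.

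| Assumed s / d (days) | Death before event, placebo vs vitamin C | Shift (days) | Significant in the direction of the shift |
|---|---|---|---|
| 7 / 3 | 30% vs 10% (every death precedes the event) | (−0.20)(−4) = +0.80 | 10%–24% against vitamin C |
| 7 / 3 | 15% vs 5% (half the deaths do) | (−0.10)(−4) = +0.40 | 5%–10% against |
| 7 / 3 | 30% vs 20% | (−0.10)(−4) = +0.40 | 5%–9% against |
| 7 / 3 | 30% vs 30% | 0 | about 2.5% each way |
| 3 / 1.5 | 30% vs 10% | (−0.20)(−1.5) = +0.30 | 9%–20% against |
| 3 / 5 | 30% vs 10% | (−0.20)(+2) = −0.40 | 8%–21% in favour |

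The nominal rate in each direction is 2.5%. These rates do not carry over to item e, which covers ventilated participants only. With an assumed 31 per arm, the first row becomes 7%–14%.

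**3. Shift when deaths are dropped.** At 30% vs 10%, up to 62 × 0.30 = 18.6 placebo and 62 × 0.10 = 6.2 vitamin C participants leave the comparison. Of the vitamin C survivors, 0.20/0.90 = 22.2% would have died on placebo. If they average 10 days against 7 (assumed), the shift is 0.222 × 3 = +0.67 day. A separate log-normal model with a mean recovery time of 96 hours shows no inflation (rejection 4%–5%) when death is unrelated to severity. When death is linked to severity, rejection is about 15%–16% at 30% vs 10%.

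**4. The remedy under the same test.** Same 7 / 3 case, no effect on recovery, 6,000 trials, follow-up to Day 28:

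- Cumulative incidence with death competing favours vitamin C in about 70% of trials at 30% vs 10%, 21%–22% at 30% vs 20%, and about 2.5% each way at equal mortality.
- The cause-specific log-rank test rejects (both directions together) in up to about 10% at 30% vs 10% and about 5%–6% at 30% vs 20%.

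**The case against.** **The t test is not itself invalid.** At equal mortality it holds its level. If death ends the clock, it validly compares mean days actually spent on pressors or in the ICU. A reader might infer that the 10%–24% are false positives in that sense. They are not; the error lies in reading the difference as slower or faster recovery. This stands, but recovery is what Aim 2 sets out to assess.

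**The replacement also carries mortality.** Cumulative incidence favours the drug far more often than the t test goes against it. This stands too. It is why cumulative incidence must not be shown alone, and why the cause-specific comparison and mortality have to accompany it.

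**Scope.** A reader might infer that none of the four items deals with death, or that item a counts death as the end of vasopressor therapy. The documents do not support either. Item b is largely settled by the use of ICU discharge in the primary endpoint. Item a can be read either way when death falls on pressors or inside the 24-hour window.

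**Size.** The power section refers to hospital mortality, and deaths after extubation, pressor liberation or ICU discharge leave a complete duration. Treating every death as preceding the event is the upper end; halving that proportion halves the shift. The headline case also pairs a large mortality benefit with no effect on recovery.

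**Stakes.** The endpoints are conditional and secondary, and mortality will be reported in the same trial. This limits the importance of the point but does not remove it.

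**Conclusion.** The point holds as a secondary-endpoint problem that should be corrected. The plan names a method that needs a number for every participant. It provides none for items c and e, is ambiguous for item a, and for item b appears to count an early death as a short stay. When mortality differs, the resulting comparison does not isolate recovery.

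The size rests on assumed durations. In the 7 / 3-day case it is 0.8 day against vitamin C at 30% vs 10% if every death comes first, about 0.4 day if half do, and nothing at equal mortality. It would be tempting to conclude that the plan is biased against vitamin C. The documents do not support that: they say nothing about when deaths occur, and if deaths last longer on support than survivors, the shift favours the drug. Nor does the point reach the primary mortality analysis or the sample size. Confidence is moderate, because the gap in the text is clear but its numerical effect is not fixed by the documents.

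**What to change.** Before unblinding, amend Sections 3.2 and 16.1 as follows.

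- For items a, c and e, and for item b redefined as ICU discharge alive, replace the t test and linear regression with time-to-event reporting that treats death as a competing event.
- Report the cause-specific comparison (speed of recovery) and the cumulative incidence (recovery while alive) together, with mortality beside them. State that neither result alone may be read as faster recovery.
- Give the censoring time for each item, and say how item a classes a death within 24 hours of stopping vasopressors.
- If the t test is kept for any item, write down at least how deaths and never-reached events are scored.

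The cost is protocol wording and a little more analysis; no participants are added. Daily chart review ends at Day 4 (Section 5.2), so later stop dates must be read at the Day 28 chart review already planned in Section 5.3. Later lactate values must be read there too, or lactate follow-up cut at 96 hours.

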2.0 Background

2.1 Significance of Research Question/Purpose:

Sepsis is defined as life threatening organ dysfunction caused by a dysregulated response to infection. Sepsis and septic shock, the latter defined as persistent hypotension refractory to volume resuscitation and requiring vasopressor therapy to maintain adequate blood pressure, are common reasons for admission to the intensive care unit¹. It is estimated that approximately 1 million Americans are diagnosed every year². Despite concerted efforts focused on early recognition and stabilization of septic patients, mortality rates of patients admitted with septic shock remain high at 25%-50%¹ and survival is still associated with significant comorbidity³. This is of particular importance when sepsis-associated organ failure is prolonged, as the extended recovery period keeps patients vulnerable to adverse effects associated with prolonged ICU stays (e.g., myopathy, delirium). All of this highlights the need for novel effective therapies.

The main tenets of therapy in sepsis have been focused on early recognition, hemodynamic stabilization (correction of low blood pressure) and antimicrobial therapies. This involves early aggressive fluid resuscitation and vasopressor therapy (medications such as epinephrine which increase blood pressure), as well as early empiric antibiotic therapy and effective source control, the latter of which consistently correlates with survival^{1,3,4}. Over the last two decades, most efforts to improve outcomes in sepsis have focused on resuscitation at the systemic level (e.g. blood pressure and cardiac output goals). Unfortunately, although several 'targeted' systemic resuscitation studies have shown promise during early studies (e.g. early goal directed therapy protocol⁵, large-scale confirmatory studies of these treatments have been disappointing⁶⁻¹⁰). As a result, renewed attention has shifted towards identification of sepsis-induced abnormalities at the cellular and microcirculation level, such as dysfunction of mitochondria (the parts of cells which generate energy), endothelium (the lining of blood vessels which plays a role in controlling blood supply to tissues) and cellular oxygen metabolism despite adequate tissue blood supply¹¹.

Therapies aiming to correct oxygen metabolism, mitochondrial, and endothelial dysfunction have been dubbed “metabolic resuscitation”^{12,13}.

2.2 Preliminary Data:

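### For the creatinine and SOFA/APACHE changes, section 16.1 neither secures adjustment for the outcome's own baseline value nor says which analysis is the main one

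*Combined protocol and SAP*

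**What the plan says.** Section 3.2 lists secondary endpoints that may be used, depending on power and final enrolment. Two of them are change scores at fixed times:

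- Item g: "Change in serum creatinine at 24, 48, 72, and 96 hours after Vitamin C (or placebo) administration compared to level at enrollment". It is limited to patients with values available and leaves out those on dialysis or renal replacement therapy.
- Item h: "Change to SOFA and/or APACHE scores from initiation of Vitamin C (or placebo) as measured at 24, 48, 72, and 96 hours".

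Section 16.1 gives the Aim 2 analysis in two sentences. The first says "Clinical outcomes at ICU discharge will be compared between groups using two-sample t test for continuous variables", with a Chi-square test for categorical variables. The second says "Multivariate linear and logistic regression analysis will be performed for continuous outcomes and dichotomous outcomes respectively to adjust for covariates".

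Neither sentence names an Aim 2 covariate or ranks one analysis above the other. The only rule for choosing covariates stands under Aim 1. It admits those that the investigators judge to affect mortality and those that differ significantly between groups at baseline. The schedule in section 5.3 includes a baseline chart review on Day 0.

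**The concern.** A t test on change subtracts the whole baseline value, which fixes the slope of follow-up on baseline at 1. If the true slope is lower, patients who start high tend to fall more whatever their treatment, and that variation stays in the comparison as noise. A chance baseline difference between arms also carries into the result. Regression with the baseline value as a covariate estimates the slope instead.

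The plan has room for such a regression but does not commit to it. If the t test is read as the main result, precision may be lost. If the regression is, its covariates can be chosen after the data are seen. Organ failure is a named outcome of Aim 2 and the arms are small (62 analysed, 70 enrolled), so both matter for how these endpoints can be interpreted.

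**Working it through.** **The plan's own figure.** The only sizing figure is for mortality: "124 patients, 62 patients in each arm", for "80% power to detect a 20 % decrease in hospital mortality between the two groups" at a "two-tailed alpha error of 0.05". The control rate is not stated. Assuming 30% against 10% (a 20-point difference):

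n per arm = [1.96 × √(2 × 0.20 × 0.80) + 0.842 × √(0.30 × 0.70 + 0.10 × 0.90)]² / 0.20² = (1.109 + 0.461)² / 0.04 ≈ 61.6, rounded up to 62.

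So the figure reproduces under that assumption. It says nothing about items g and h, for which the documents give no SD, correlation or power.

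**Inputs for items g and h (all assumed).**

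- r, the correlation between baseline and follow-up: 0.3 to 0.8.
- k, the follow-up SD divided by the baseline SD: 0.75 to 1.5.

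**Formulas, at one time point, in units of the baseline variance.**

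- Change score: 1 + k² − 2rk.
- Baseline-adjusted: k²(1 − r²).
- Difference: 1 − 2rk + r²k² = (1 − rk)².
- Proportional reduction: (1 − rk)² / (1 + k² − 2rk).

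The numerator is a square, so the reduction cannot be negative. It is zero when rk = 1, that is, when the true slope is already 1. With k = 1 it simplifies to (1 − r)/2.

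**Worked cases.**

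- k = 1, r = 0.3: 0.70² / 1.40 = 0.49 / 1.40 = 35%.
- k = 1, r = 0.8: 0.20² / 0.40 = 0.04 / 0.40 = 10%.
- k = 1.25, r = 0.3: 0.625² / 1.8125 = 0.3906 / 1.8125 = 21.6%.
- k = 1.25, r = 0.8: rk = 1, so 0%.
- k = 0.75, r = 0.3: 0.775² / 1.1125 = 0.6006 / 1.1125 = 54%.

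**Reduction in variance over the range.**

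| r | k = 0.75 | k = 1 | k = 1.25 | k = 1.5 |
|---|---|---|---|---|
| 0.3 | 54.0% | 35% | 21.6% | 12.9% |
| 0.5 | 48.1% | 25% | 10.7% | 3.6% |
| 0.6 | 45.7% | 20% | 5.9% | 0.7% |
| 0.7 | 44.0% | 15% | 1.9% | 0.2% |
| 0.8 | 44.1% | 10% | 0.0% | 4.7% |

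A simulation with 62 per arm and k = 1 gave 34.6% at r = 0.3 and 9.4% at r = 0.8, in line with the formula.

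**Source of the gain.** The whole reduction comes from the baseline covariate at a single time point. None of it needs a repeated-measures model.

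**Timing.** Section 3.2 fixes items g and h at 24, 48, 72 and 96 hours after the start of infusion. Section 16.1 compares Aim 2 outcomes at ICU discharge. These are different times, and the analysis text does not say how the four values are to be used.

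**The case against.** The strongest reply is that adjustment is already planned. Regressing the change on treatment and baseline gives the same treatment estimate as regressing the follow-up value on them. If the baseline value is among the covariates, the gain over the planned regression at that time is therefore zero. The Aim 1 rule, if carried over, could admit baseline SOFA, APACHE or creatinine under either limb. This stands as far as it goes: a reader might infer from the t-test sentence that the plan makes no adjustment, and the next sentence shows otherwise. But the rule is written for Aim 1 only, and even if borrowed it permits the baseline value without requiring it.

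Other stronger readings also go beyond the documents:

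- *Four separate t tests per outcome.* This follows only from joining section 3.2 to section 16.1, which speaks of ICU discharge and never states four tests.
- *A gain of 10% to 35%.* That range needs equal SDs as well as the assumed correlations. Other SD ratios give anything from about 0% to 54%.
- *An equivalent number of patients saved.* The 124 was sized for mortality. Item g also drops dialysis patients and those without values, so its own number is unknown.
- *One repeated-measures model at no cost.* Such a model needs a covariance structure and a missing-at-random assumption, and some values here will be missing through death or discharge. Separate t tests or regressions face the same missing values, and the plan does not say how they are handled.

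Finally, these are two items in an optional list without a power calculation. That limits the weight of the point but does not remove it.

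**Conclusion.** The point holds in a limited form. The plan leads with a two-sample t test and follows with a regression whose covariates and status are unstated, so baseline adjustment of items g and h is possible but not secured. Making it the main analysis is a better method than the t test on change, using data already collected, and not merely a missing detail.

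Under a linear model, and apart from one degree of freedom, it is never less precise. How much more precise cannot be known from the documents. For assumed r of 0.3 to 0.8 the variance reduction is 35% to 10% at k = 1, about 22% to 0% at k = 1.25, about 13% to near 0% at k = 1.5, and 44% to 54% at k = 0.75. The mortality analysis and the planned 124 analysed and 140 enrolled do not change.

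**What to change.** In section 16.1, for items g and h:

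1. Make the planned linear regression the main analysis at each of 24, 48, 72 and 96 hours, with treatment and the baseline value of the same outcome as covariates.
2. Report the adjusted difference and 95% CI at each time, and label the t test on change as supportive.
3. Reconcile the comparison at ICU discharge with the 24 to 96 hour times in section 3.2.
4. A single repeated-measures model is optional. If it is used, state the main contrast and how death and discharge are handled.

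Steps 1 to 3 cost a few sentences and one extra model term: no new data, no extra patients, and one degree of freedom. Step 4 has a small further cost: a covariance structure to choose and a missing-at-random assumption to defend.
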